Blood Sample for Nivolumab PK and Nivolumab ADA Pre-dose ^{1,2,4}		X		X	X	X	X ⁴
Blood Sample for Ipilimumab PK and Ipilimumab ADA Pre-dose ^{1,2,5}		X		X	X	X	
Tissue Biopsy for Ivosidenib PK Pre-dose ^{6,7}	X						
Tissue Biopsy for Ivosidenib PK Post-dose ⁶					X (± 7 days for tissue sample only)		
Tissue Biopsy for PD (2-HG) Pre-dose ^{6,7}	X						
Tissue Biopsy for PD (2-HG) Post-dose ⁶					X (± 7 days for tissue sample only)		
Blood Sample for Nivolumab and Ipilimumab PK Post-dose ⁸		X (EOI)					
Blood Sample for Ivosidenib PK Post-dose ⁸							
2 hr post-dose						X	
3 hr post-dose						X	
4 hr post-dose						X	
6 hr post-dose						X	

Abbreviations: 2-HG = 2-hydroxyglutarate; ADA = anti-drug antibody; D = Day; EOI = End of Infusion; PD = pharmacodynamic; PK = pharmacokinetic.

1. On the days when pre-dose samples are to be collected, subjects should be instructed to not take that day's dose of ivosidenib, nivolumab or ipilimumab dose, until PK/PD samples have been collected (ivosidenib dose is to be administered in the clinic). If it is known that a dose is going to be delayed, then collect the pre-dose samples just prior to the delayed dose. However, if a pre-dose sample is collected, but the dose is subsequently delayed, do not collect an additional pre-dose sample.
2. Pre-dose blood samples for ivosidenib, nivolumab, and ipilimumab PK, ADA, and 2-HG are to be collected from all subjects within 30 minutes before ivosidenib, nivolumab, and ipilimumab dose. All pre-dose samples may be collected in one blood draw.
3. Pre-dose blood samples for ivosidenib PK and 2-HG are to be collected on C1D1, C1D15, C2D1, C3D1, C4D1, C5D1, and Day 1 of every cycle through Cycle 13, and Day 1 of every other cycle thereafter (e.g., Cycles 15, 17, etc.).
4. Pre-dose blood samples for nivolumab PK and nivolumab ADA are to be collected on C1D1, C2D1, C3D1, C4D1, and Day 1 of every 4 cycles up to 2 years (e.g., C8D1, C12D1, etc.)
5. Pre-dose blood samples for ipilimumab PK and ipilimumab ADA are to be collected on C1D1, C2D1, C3D1, and C4D1.
6. Refer to the lab manual for details on tumor biopsy collection.
7. If a subject cannot undergo a biopsy at Screening, archived fresh-frozen tumor biopsy, if available, can be used for the measurement of baseline 2-HG.

8. Post-dose blood samples to be collected within ± 10 minutes of the specified time.

A mean volume of blood collected for all type of analyses is shown in Table (4.1.2) 4.

Table (4.1.2) 4 - Mean Blood Volume for CL1-95031-006

Visit/Cycle	Total volume/visit (mL)	Total volume/cycle (mL)
Screening	39.7	39.7
C1D1	53	67
C1D15	14	
C2D1	60	79
C2D15	19	
Cycle 3	48	48
Cycle 4	48	48
Cycle 5	41	41
Cycle 6	30	30
ODD cycles (C7, C9, C1, etc.)		9
Even cycles (C8, C10, C12, etc.)	from 3 to 27 mL depending on assessments, except for cycles Cycle 14 and Cycle 22 where no blood draws are planned	
EOT	32	32

4.1.3. Dose Justification

4.1.3.1. Dose Justification for Ivosidenib

The selection of the 500 mg QD clinical dose of ivosidenib was based on PD (2-HG suppression), PK, safety, and efficacy data from the Phase 1 (AG120-C-002) and Phase 3 (AG120-C-005) studies. The 500-mg dose level is also the approved dose for the US Marketing Authorization of ivosidenib for the CCA indication ([TIBSOVO®, 2021](#)).

Plasma ivosidenib exposure increases in a less than dose-proportional manner from 200 mg to 1,200 mg QD, with exposure plateauing at daily doses above 500 mg QD. Mean plasma 2-HG concentrations for subjects with CCA were elevated at baseline (ranging from 222 to 5,220 ng/mL). After multiple doses of ivosidenib, plasma 2-HG levels were substantially reduced to concentrations similar to healthy subjects ([CCI](#) ng/mL). No additional 2-HG suppression was observed at doses > 500 mg QD compared with 500 mg QD, while doses < 500 mg QD were associated with lower levels of suppression. In tumor biopsies of subjects with CCA, near maximal mean reduction in 2-HG concentrations of 82.2% (coefficient of variation, 32.4%) was observed at the 500 mg QD dose. Analysis of the relationship between ivosidenib exposure and QT interval prolongation demonstrated that the risk of QT interval prolongation increases with increases in plasma C_{max} and suggests that doses higher than 500 mg QD may be associated with longer QT intervals.

In Study AG120-C-002, there have been minimal dose interruptions, and no apparent dose relationship for any commonly reported TEAEs or Grade ≥ 3 TEAEs. No DLTs were reported in the study. The Phase 3 study, AG120-C-005, demonstrated that as a single agent in subjects with advanced CCA, ivosidenib was generally well tolerated with a manageable safety profile.

The efficacy of ivosidenib at the recommended 500 mg QD dose was supported by the efficacy results from Study AG120-C-002. As of the 16 January 2019 cutoff date, the median OS was [CCI](#) at the 500 mg QD level.

The efficacy of ivosidenib at the recommended dose of 500 mg QD in subjects with CCA was established based upon the efficacy results of ivosidenib from Study AG120-C-005. Improvement in PFS by Independent Review Committee assessment was demonstrated for subjects randomized to treatment with ivosidenib compared with placebo (1-sided p-value < 0.0001; HR = 0.37; 95% CI: 0.25, 0.54). A benefit in OS was also observed in favor of ivosidenib.

In summary, the PK and PD profiles along with the safety and efficacy results of ivosidenib in subjects with CCA support selection of the 500 mg QD dose.

4.1.3.2. Dose Justification for Nivolumab and Ipilimumab Combination

The nivolumab and ipilimumab combination is currently approved in the US and EU in multiple tumor types, including melanoma, NSCLC, RCC, and CRC using a regimen of either nivolumab [redacted] mg/kg and ipilimumab [redacted] mg/kg or nivolumab [redacted] mg/kg and ipilimumab [redacted] mg/kg.

NIVO has a wide therapeutic index with no maximum tolerated dose identified at doses up to 10 mg/kg Q2W. Nivolumab PK was assessed using a population PK approach for both single-agent nivolumab and nivolumab with ipilimumab. When nivolumab [redacted] mg/kg was administered in combination with ipilimumab [redacted] mg/kg, the clearance (CL) of nivolumab was increased by 29%, and the CL of ipilimumab was unchanged compared with nivolumab administered alone. When nivolumab [redacted] mg/kg was administered in combination with ipilimumab [redacted] mg/kg, the CL of nivolumab and ipilimumab were unchanged. Additionally, the presence of anti-nivolumab antibodies increased the CL of nivolumab.

Subjects enrolled in this study will receive ivosidenib 500 mg QD in combination with nivolumab [redacted] mg/kg and ipilimumab [redacted] mg/kg concurrently [redacted]. The dosing regimen for nivolumab [redacted] mg/kg and ipilimumab [redacted] mg/kg was selected based on the encouraging clinical activity observed in previously treated BTC ([Klein et al, 2020](#)) and the current approval for this dosing regimen in advanced RCC and metastatic CRC. Additionally, the lower dose of ipilimumab ([redacted] mg/kg) provides a more manageable safety profile for this subject population.

4.1.3.3. Dose Justification for Nivolumab Flat Dose

After initiation of treatment and completion of the first [redacted] doses of nivolumab and ipilimumab combination, subjects will receive a flat dose of nivolumab [redacted] mg [redacted] for up to a maximum of 24 months. Relatively flat Exposure-Response (E–R) relationships were observed for safety across tumor types as monotherapy and in combination with ipilimumab which suggests that no additional washout is warranted before starting the NIVO 480 mg Q4W maintenance dose ([Zhao et al, 2020](#)).

Nivolumab PK has been extensively studied in multiple tumor types, including melanoma, NSCLC, RCC, cHL, SCCHN, CRC, and urothelial carcinoma and has been safely administered at doses up to 10 mg/kg once every 2 weeks (Q2W). Nivolumab monotherapy was originally approved as a body-weight based dose of 3 mg/kg Q2W and was updated to 240 mg Q2W or 480 mg Q4W in multiple indications ([OPDIVO, 2020](#)). The less frequent 480 mg Q4W dosing regimen can reduce the burden to subjects of frequent, lengthy intravenous (IV) treatments and allow combination of nivolumab with other agents using alternative dosing regimens.

4.1.4. Safety Lead-in Phase

4.1.4.1. Dose Administration Schedule

The Safety Lead-in phase will evaluate the safety and tolerability of ivosidenib in combination with nivolumab and ipilimumab in order to determine the RCD. This phase will enroll approximately 6-12 subjects with nonresectable or metastatic CCA with an IDH1 mutation.

The first 6 subjects enrolled in the Safety Lead-in phase will receive a dose of 500 mg QD of ivosidenib in combination with nivolumab [REDACTED] mg/kg and ipilimumab [REDACTED] mg/kg [REDACTED] followed by nivolumab at [REDACTED] mg [REDACTED] until progression (up to a maximum of 24 months). Depending on the DLT evaluation by the DRT, an alternative dose of 250 mg QD of ivosidenib, with the same doses of nivolumab and ipilimumab may be evaluated. A total of 12 DLT-evaluable subjects could be enrolled.

DLTs will be evaluated through Cycle 2 (*i.e.*, during the first 42 days, 21 days/cycle). DLT evaluable is determined by subjects who have received the combination therapy and experienced a DLT through Cycle 2 or who have received at least 2 doses of nivolumab and ipilimumab, respectively, and at least 75% of ivosidenib at the assigned dose through Cycle 2 without experiencing a DLT through Cycle 2. A minimum of 6 DLT-evaluable subjects will be required to evaluate the safety and tolerability of the combination.

Subjects who are not DLT evaluable will be replaced. A DRT composed of Sponsor medical, safety, and statistical representatives, together with Principal Investigator(s), will review the available safety data when at least 6 DLT-evaluable subjects have completed at least 2 cycles of treatment or experienced a DLT within the first 2 cycles.

On days when nivolumab and ipilimumab are administered, the ivosidenib dose will be administered in the clinic.

4.1.4.2. DLT Definition

All toxicities will be graded using the National Cancer Institute Common Terminology Criteria for Adverse Events (NCI CTCAE) Version 5.0 based on the Investigator assessment. The DLT window of observation will be the first 42 days of dosing (*i.e.*, Cycles 1 and 2) of the Safety Lead-In phase. The occurrence of any of the following toxicities during the first 42 days of dosing (*i.e.*, through Cycle 2) will be considered a DLT if assessed as unrelated to disease progression, intercurrent illness, or concomitant medications and considered to be related to study treatment by the Investigator.

In order to be evaluable for DLT, a subject must have had a DLT during Cycle 1 or 2, or have received 75% or more of the planned doses of ivosidenib and 2 full doses of nivolumab and ipilimumab through Cycle 2 and have not experienced a DLT. The subject must also be considered by the Investigator and Sponsor to have sufficient safety data available to conclude that a DLT did not occur.

Any of the following will be considered as DLTs that may be applicable for immuno-oncology (IO) therapy and ivosidenib:

- Any Grade \geq 4 irAE.
- Any Grade 3 irAE (excluding colitis, pneumonitis, or carditis) that does not improve to Grade 2 within 7 days after onset of the event despite optimal medical management including systemic corticosteroids or does not improve to Grade \leq 1 or baseline within 14 days.
- Any Grade \geq 3 colitis.
- Any Grade 3 non-infectious pneumonitis irrespective of duration.
- Any Grade \geq 2 pneumonitis that does not resolve to Grade \leq 1 within 7 days of the initiation of maximal supportive care.
- Any Grade \geq 2 myocarditis.
- Any Grade \geq 2 neurological toxicity including Guillain-Barre syndrome, myasthenia gravis, encephalitis, and myelitis.
- AST or ALT $> 3 \times$ the upper limit of normal (ULN) with concurrent increase in total bilirubin $> 2 \times$ ULN without evidence of cholestasis or alternative explanations, *e.g.*, viral hepatitis, disease progression in the liver (Hy's law).
- Any Grade \geq 3 non-irAE, except for those listed below.
- Any death unless related to disease progression, intercurrent illness, concomitant medications, or extraneous causes.

The DLT definition excludes the following conditions:

- Grade 3 QTc prolongation resolving to Grade 1 within 7 days.
- Grade 3 fatigue lasting \leq 7 days.
- Grade 3 endocrine disorder (thyroid, pituitary, and/or adrenal insufficiency) that is managed with or without systemic corticosteroid therapy and/or hormone replacement therapy and the subject is asymptomatic.
- Grade 3 inflammatory reaction attributed to a local anti-tumor response (*e.g.*, inflammatory reaction at sites of metastatic disease, lymph nodes).
- Concurrent vitiligo or alopecia of any CTCAE grade.
- Grade 3 or 4 neutropenia that is not associated with fever or systemic infection that improves by at least 1 grade within 7 days. Grade 3 or Grade 4 febrile neutropenia will be a DLT regardless of duration or reversibility.
- Grade 3 or 4 lymphopenia.
- Isolated Grade 3 thrombocytopenia that is not associated with clinically significant bleeding and does not require medical intervention.
- Isolated Grade 3 electrolyte abnormalities that are not associated with clinical signs or symptoms and are reversed with appropriate maximal medical intervention within 3 days.
- Isolated Grade 3 amylase or lipase abnormalities that are not associated with clinical signs/symptoms or findings on imaging consistent with pancreatitis.

4.1.4.3. DLT Management

Ivosidenib, nivolumab, and ipilimumab must be immediately interrupted for any subject who experiences a DLT. If a DLT occurs, the subject should be withdrawn from all 3 drugs unless in the opinions of the Investigator, the subject is deriving clinical benefit and the AE can be managed without recurrence, and with Sponsor approval. If ivosidenib is resumed following a DLT, it should be resumed at a reduced dose (250 mg) after the AE has resolved to Grade 1 or

baseline, with approval from the Sponsor. If nivolumab and/or ipilimumab is resumed, it will be at the original starting dose and frequency without modification.

4.1.4.4. Reporting of DLT

All DLTs will be reported to I.R.I.S. within 24 hours after the Investigator becomes aware via the DLT form in the electronic case report form (eCRF). After completing the DLT form, the Investigator must also complete the Adverse Event page of the eCRF without waiting for the results of the clinical outcome or of additional investigations. When the DLT form is submitted, an email will be immediately and automatically sent to the Sponsor.

If the eCRF is unavailable when the Investigator is informed of the DLT, the Investigator should:

- Report the DLT on a paper DLT form.
- Send the form by email immediately to I.R.I.S. at the following address: *[contact]*.

As soon as the eCRF becomes available, the site must enter the data in the eCRF.

4.1.4.5. Decision Process and Decision Rules

Subjects will receive a dose of 500 mg QD of ivosidenib in combination with nivolumab [REDACTED] mg/kg and ipilimumab [REDACTED] mg/kg CCI [REDACTED] followed by nivolumab at [REDACTED] CCI mg CCI until progression (up to a maximum of 24 months).

At the end of Cycle 2, if $\geq 33\%$ of DLT-evaluable subjects have experienced a DLT, further dosing in that cohort will be halted and the dose of ivosidenib will be reduced to 250 mg for all subjects in that cohort. The DRT may recommend enrolling up to an additional 6 subjects to receive ivosidenib at a 250 mg QD dose level, and the same dose stopping rules will be applied after review of the safety data through Day 42 (through Cycle 2). The DRT may decide to cease enrollment in a dosing cohort if fewer than 2 subjects experience DLTs but the nature of the event(s) is deemed a significant risk to subjects at that dose level. Because the immune-modulating regimen of nivolumab and ipilimumab itself may give rise to Grade 3 or 4 toxicity, the DRT will also consider the aggregate treatment-emergent data in relation to the known toxicity profile of nivolumab and ipilimumab and determine the acceptability of the safety profile of the combination. If 0 or 1 of the 6 evaluable subjects experiences a DLT during the first 2 cycles at the 500 mg or the 250 mg QD dose level, the study may proceed to the Expansion phase.

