10.1.5. Analysis of Primary Endpoints

10.1.5.1. Safety Lead-in Phase: Estimation of the RCD - Ivosidenib in Combination with Nivolumab and Ipilimumab

One of the primary endpoints during the Safety Lead-in phase is DLT through Cycle 2. The criteria of DLT rate < 33% will be used to determine the RCD for ivosidenib in combination with nivolumab and ipilimumab. DLT rate will be calculated based on the DLT-Evaluable Set by dose level. The DRT will review the aggregate treatment-emergent safety data in addition to DLTs to determine the RCD.

10.1.5.2. Expansion Phase: Objective Response per Investigator Assessment of Anti-tumor Activity (Using RECIST v1.1)

The primary endpoint during the Expansion phase is the objective response per RECIST v1.1 for solid tumors [Appendix 5]) (Eisenhauer *et al*, 2009).

The primary estimand of interest is the ORR. The attributes of the primary estimand are defined as follows:

- Treatment: ivosidenib plus nivolumab and ipilimumab.
- Population: Safety Analysis Set.
- Variable: ORR (for the primary efficacy endpoint).
- Summary measure: objective response (Yes, No).
- Intercurrent events (IE):

1. Early treatment discontinuation
2. Administration of further anti-cancer therapy

Primary analysis

The primary analysis for the primary endpoint of objective response will be based on the Safety Analysis Set.

The ORR will be calculated as the proportion of participants who achieve confirmed CR or PR with the 2-sided exact binomial 95% CI by cohort. Participants treated at the RCD and enrolled during the Safety Lead-in phase will be pooled with those receiving the same dose of ivosidenib during the Expansion phase for each cohort as appropriate.

Supportive Analysis

A supportive analysis for the primary endpoint of objective response will be based on the Response-Evaluable Set.

Additional sensitivity analysis may be conducted based on retrospective central review if available.

Other estimands of interest for the primary endpoint of objective response may be analyzed as appropriate.

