10.2.1. Safety Lead-in Phase

During the Safety Lead-in phase, one of the primary endpoints is DLT through Cycle 2. Approximately 6 to 12 DLT-evaluable subjects will be enrolled to be evaluated at up to 2 dose levels of ivosidenib in combination with nivolumab and ipilimumab:

- 500 mg QD: Initially approximately 6 DLT-evaluable subjects will be examined. If at least 2 DLTs from the 6 subjects are observed, a lower dose of 250 mg QD ivosidenib will be considered for assessment with consideration of the overall safety data from the 6 subjects.
- 250 mg QD: Another approximately 6 DLT-evaluable subjects will be examined.

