5. STATISTICAL ANALYSES

The study stopped enrollment after enrolling 7 patients for the Safety Lead-in phase and did not proceed to the Expansion phase, therefore limited listings will be generated as appropriate. Tables and figures will not be generated in general, unless specifically mentioned.

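### The lead-in dose rule is given as a percentage and as a count out of six; the two agree on two subjects with a DLT only when exactly six are evaluable, and no passage says which governs above six.

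*Protocol*

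**What the plan says.** The protocol states the Safety Lead-in dose decision in two forms.

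**Percentage form, with no fixed denominator**
- Section 4.1.4.5 (repeated in the synopsis): if at least 33% "of DLT-evaluable subjects have experienced a DLT, further dosing in that cohort will be halted".
- Section 10.1.5.1: "The criteria of DLT rate < 33% will be used to determine the RCD". On the denominator: "DLT rate will be calculated based on the DLT-Evaluable Set by dose level".

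**Count form, tied to six**
- Section 4.1.4.5 (repeated in the synopsis): "If 0 or 1 of the 6 evaluable subjects experiences a DLT during the first 2 cycles", at either dose level, the study may move to the Expansion phase.
- Section 10.2.1: "If at least 2 DLTs from the 6 subjects are observed", the 250 mg level is to be considered, taking overall safety into account. This clause counts DLTs, not subjects with a DLT.
- Section 4.1.4.5 also uses two as a boundary without any denominator: "The DRT may decide to cease enrollment in a dosing cohort if fewer than 2 subjects experience DLTs", where the nature of the event is judged a significant risk.

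**Number evaluable**
- Section 4.1.4.1: "A minimum of 6 DLT-evaluable subjects will be required to evaluate the safety and tolerability of the combination". The Data Review Team (DRT) meets once at least six are evaluable, and Section 10.2.1 plans approximately six per dose level. No maximum per dose level is stated.
- SAP Section 5: "The study stopped enrollment after enrolling 7 patients for the Safety Lead-in phase". The SAP repeats the definition of the DLT-Evaluable Set (Section 3.1) and plans a listing of DLTs (Section 5.4.1.1). It gives no DLT threshold.

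**The concern.** Determining the RCD is part of the lead-in's primary objective, and this is its decision rule. A percentage and a count are interchangeable only at the sample size for which the count was written. The protocol allows that size to be exceeded, and overshoot is easy to foresee: non-evaluable subjects are replaced and about 10 sites are planned, so a replacement can be enrolled while another subject's status is still open. Once a seventh subject is evaluable, the outcome of two subjects with a DLT is read differently according to the sentence used. A DRT would then have to choose between the readings after seeing the data.

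**Working it through.** **Inputs.** Halt at 33% or more (4.1.4.5); RCD criterion below 33% (10.1.5.1); proceed condition of 0 or 1 of six (4.1.4.5); at least six evaluable per dose level (4.1.4.1). The true DLT rates used below are my assumptions; the documents give none. The protocol says that the sample sizes do not rest on power or type I error, so there is no planned operating characteristic to reproduce.

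**Step 1: the plan's own case, n = 6.** 1/6 = 16.7%, below 33%, and within 0 or 1. 2/6 = 33.3%, at or above 33%, and outside 0 or 1. The two forms agree exactly.

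**Step 2: n = 7 and n = 8.** The count boundary is carried over unchanged as at most one subject.

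| Evaluable | Subjects with a DLT | Proportion | Percentage form | 0-or-1 condition |
|---|---|---|---|---|
| 7 | 1 | 14.3% | no halt, below 33% | met |
| 7 | 2 | 28.6% | no halt, below 33% | **not met** |
| 7 | 3 | 42.9% | halt | not met |
| 8 | 1 | 12.5% | no halt, below 33% | met |
| 8 | 2 | 25.0% | no halt, below 33% | **not met** |
| 8 | 3 | 37.5% | halt | not met |

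The conflict is confined to exactly two subjects with a DLT.

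**Step 3: how often it could matter.** Treat the DLT count as the whole decision and as binomial with true rate p. The count form clears with probability P(X ≤ 1) = (1−p)^n + n·p·(1−p)^(n−1). At n = 7 and 8 the percentage form clears with P(X ≤ 2), which adds P(X = 2) = C(n,2)·p²·(1−p)^(n−2).

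For n = 7 and p = 0.33: 0.67⁷ + 7 × 0.33 × 0.67⁶ = 0.061 + 0.209 = 0.270. P(X = 2) = 21 × 0.33² × 0.67⁵ = 0.309. The sum is 0.578 (from unrounded terms).

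| Assumed true rate | n = 6, both forms | n = 7, percentage | n = 7, count | n = 8, percentage | n = 8, count |
|---|---|---|---|---|---|
| 20% | 65.5% | 85.2% | 57.7% | 79.7% | 50.3% |
| 33% | 35.8% | 57.8% | 27.0% | 47.6% | 20.1% |
| 40% | 23.3% | 42.0% | 15.9% | 31.5% | 10.6% |

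**Step 4: the unit in Section 10.2.1.** Because that clause counts DLTs, one subject with two separate DLTs would satisfy its wording, although the proportion of subjects is 1/6 = 16.7%. This difference does not depend on n exceeding six.

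**The case against.** The strongest reply is that the count clauses only restate the percentage rule at the planned size of six and are silent above it. The proceed clause is permissive and refers to six subjects; it does not say that the study may proceed *only* then. The one mandatory rule is the halt at 33% or more, which is defined for any number evaluable. This limits the point: at 7 or 8, two subjects with a DLT leave the proceed condition unmet, which is not the same as an explicit failure of the dose. It does not remove the point. If the count clauses are silent, the explicit condition for proceeding disappears above six and nothing says that the percentage takes over. The clause on fewer than two subjects, which has no denominator, also suggests that two is the boundary whatever the number evaluable.

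A second reply is that the six might mean the first six. The text does not say so. On that reading, with two of seven having a DLT, the conflict is certain only when both are among the first six: C(6,2) = 15 of C(7,2) = 21 arrangements.

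Third, the DRT has discretion. That is correct, and it rules out two stronger readings. A rate below 33% does not by itself make a dose the RCD, because Section 10.1.5.1 has the DRT weigh overall safety as well. Nor does Section 10.2.1 impose de-escalation; it says that 250 mg is to be considered. But discretion about other safety data does not tell the DRT which DLT threshold it starts from.

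Fourth, the unit mismatch may be loose wording. Section 4.1.4.3 interrupts all three drugs at a DLT, with withdrawal the default, so two separate DLTs in one subject are less likely. It is a minor part of the point.

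**Conclusion.** The point stands as an inconsistency between stated criteria for the lead-in's primary decision when more than six subjects are evaluable. At 7 or 8 evaluable, two subjects with a DLT meet the rate criterion and avoid the halt but do not meet the stated proceed condition, and the documents do not settle which governs. At an assumed true DLT rate of 33%, the chance of clearing with 7 evaluable differs by about 31 percentage points between the forms (57.8% and 27.0%); at 40%, by about 26 (42.0% and 15.9%). These figures ignore the DRT's wider safety review, so they describe the gap between the rules and not the behaviour of the whole process.

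A reader might infer from the SAP's 7 enrolled that the conflict occurred. The documents do not support this. Seven enrolled is compatible with six evaluable plus one replaced subject, and neither the number evaluable nor any DLT result is reported. Because enrolment stopped in the lead-in and no Expansion phase follows, what remains at stake is mainly how the DLT result is described. That still matters: the SAP keeps RCD determination in the primary objective (Section 1.1) and the DLT-Evaluable Set as the primary set for it (Section 3.1), without a threshold.

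**What to change.** The sponsor should reconcile the synopsis and Sections 4.1.4.5, 10.1.5.1 and 10.2.1 into one rule. It should be expressed in subjects with at least one DLT and stated for each possible number of evaluable subjects, for example as a short table. Which threshold is right is for the sponsor to settle; this review does not say.

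Since the trial has stopped, the SAP is where a change still has effect. Section 5.1.1 already plans to describe the size of each analysis set. Section 5.4.1.1 should add the number evaluable at each dose level beside the DLT listing, and say which criterion and which denominator apply when the results of the 7 enrolled are reported.

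The cost is wording in four places in the protocol and a sentence or two in the SAP. No further subjects or data are needed.
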